12.2.7 Calculation and derivation of organ failure assessment

Failure of an organ system will be recorded the first time any of the criteria specified in the individual components of the modified SOFA score are >1 after the start of study drug up to Day 15 (over 14 days). Organ failure-free days will be designated for those days when the organ system modified SOFA score is ≤ 1 . The worst BP and saturation values of the day should be used, and if a drug holiday or no value is collected, the last assessment performed should be the value for that day.

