5.1 Inclusion criteria

For inclusion in the study patients must fulfil the following criteria.

1. Patients undergoing a first episode of sepsis during this hospitalisation (including transfer from another hospital).
2. Objective clinical evidence of infection; at least 1 of the following (see also inclusion criterion 5). Including:
 - Perforated viscus.
 - WBC and/or pathogens in a normally sterile body fluid.
 - Radiographic evidence of pneumonia.
 - Signs of a local source of infection such as cellulitis.
 - A syndrome associated with a high risk of infection (eg, ascending cholangitis).
 - Positive culture from blood or from another normally sterile body fluid prior to study drug administration.
 - Evidence of an infecting organism such as pneumococcal antigen or Legionella antigen.
3. Patients must meet at least 2 of the following 4 SIRS criteria at least one of which must be the core temperature criterion or the WBC criterion (see also inclusion criterion 5); these criteria do not have to be met simultaneously; the actual values and the date and time that the criteria were met will be collected.
 - Hypothermia by core temperature $<36^{\circ}\text{C}$, or hyperthermia $>38^{\circ}\text{C}$ measured via any means.
 - Heart rate (HR) >90 beats per minute.
 - Respiratory rate (RR) >20 breaths/minute related to septic event or partial pressure of arterial carbon dioxide (PaCO₂) <32 mmHg related to septic event or requiring mechanical ventilation related to septic event.
 - Total WBC absolute count >12000 cells/mm³ or <4000 cells/mm³. In the presence of granulocyte-stimulating factor, for those patients whose WBC absolute count is >12000 cells/mm³, they must have a fever and at least one other criterion (RR or HR).
4. Patients must meet criteria for cardiovascular and/or respiratory dysfunction (see also inclusion criterion 5). Newly developed organ failures must be due to the acute

THIS IS A PRINTED COPY OF AN ELECTRONIC DOCUMENT. PLEASE CHECK ITS VALIDITY BEFORE USE.

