septic process and not be explained by a chronic condition or by effects of concomitant therapy. Time of onset of the protocol qualifying organ dysfunction/failure will be recorded. For cardiovascular dysfunction, the time of organ dysfunction/failure is defined as the time of initiation of vasopressors. The time of pulmonary dysfunction/failure is defined as the time that the patient meets the appropriate $\text{PaO}_2/\text{FiO}_2$ (or $\text{SpO}_2/\text{FiO}_2$ ratio) ratio while on mechanical ventilation (for organ dysfunction/failure definitions, see [Table 2](#)). An arterial blood gas or recording of the patient's SpO_2 value within 2 hours of intubation will be required otherwise the 24 hour clock will begin at the time of intubation. Patients who have been on mechanical ventilation for more than 48 hours prior to the CCC call cannot use pulmonary dysfunction as the qualifying organ failure. These patients can be enrolled if they meet criteria for cardiovascular dysfunction.

Table 2 Organ dysfunction/failure definitions

System / organ	Definition
Cardiovascular System	
Hypotension, as defined as a systolic blood pressure <90 mmHg, or a mean arterial blood pressure ≤ 65 mmHg requiring vasopressors despite a) a volume infusion of 20 mL/kg crystalloid or colloid equivalent over 4-6 hours before randomisation or b) 30mL/kg crystalloid or colloid equivalent in the 24 hours prior to randomisation after consultation with the CCC.
 
NOTE 1: If hypotension and vasopressor requirement is in the setting of intubation, the patient must still be vasopressor-dependent 1 hour after intubation. Patients requiring vasopressors prior to intubation are eligible for the study.
 
NOTE 2: 10 mL/kg of colloids = 20 mL/kg crystalloids.

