Pulmonary Dysfunction	
Pulmonary dysfunction is defined as the patient requiring mechanical ventilation related to the septic process and having a $\text{PaO}_2/\text{FiO}_2 \leq 300$ (or $\text{SpO}_2/\text{FiO}_2 < 357$). However, if lung is the primary site of infection then $\text{PaO}_2/\text{FiO}_2$ must be <200 (or $\text{SpO}_2/\text{FiO}_2 < 214$). Arterial blood gas measurements are preferred but if unobtainable, SpO_2 will be sufficient. SpO_2 should be obtained for all patients. If $\text{SpO}_2/\text{FiO}_2$ is being used, saturation must be $\leq 97\%$. Otherwise, SpO_2 should be measured at a different FiO_2 if clinically appropriate, or arterial blood gases should be obtained and $\text{PaO}_2/\text{FiO}_2$ used instead.
 
Patients who have been on mechanical ventilation for more than 48 hours prior to the CCC call cannot use pulmonary dysfunction as the qualifying organ failure. These patients can be enrolled if they meet criteria for cardiovascular dysfunction.

Abbreviations: CCC = Clinical Co-ordinating Centre; FiO_2 = fraction of inspired oxygen; PaO_2 = partial pressure of arterial oxygen.; SpO_2 = Oxygen saturation by pulse oximetry.

5. Sepsis (infection + SIRS criteria) must be present prior to cardiovascular and/or respiratory failure. SIRS criteria and cardiovascular and/or respiratory failure do not need to be present simultaneously but SIRS criteria must have been demonstrated at some time within the 24 hours preceding the initial cardiovascular and/or respiratory failure, even if SIRS criteria have been present for more than 24 hours. In the case where the patient first presents with cardiovascular and/or

respiratory dysfunction due to infectious process (eg, a new hospital admission), SIRS criteria must be met prior to study drug administration.

Study drug administration must occur within 24 hours after the onset of qualifying cardiovascular and/or respiratory failure.

In addition to the above criteria, for inclusion in the genetic and/or biomarker research undertaken in this study, patients must fulfil the following criterion:

1. Provision of informed consent for genetic and/or biomarker research (by the patient or his/her legally authorised representative).

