7.6.5 Organ failure assessment

Organ failure developing after study entry, regardless of cause, will be assessed using the modified SOFA score at the timepoints specified in [Table 1](#).

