7.6.6 Septic shock

Occurrence of septic shock will be collected as part of organ failure outcome data.

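### The rule for organ failure after study entry has no baseline condition, so the system that qualified the patient will usually be recorded as a post-entry failure

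*Protocol*

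**What the plan says.** Protocol section 7.6.5 states the purpose: "Organ failure developing after study entry, regardless of cause, will be assessed using the modified SOFA score".

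Section 12.2.7 gives the derivation: "Failure of an organ system will be recorded the first time any of the criteria" in the individual modified SOFA components exceed 1, counting from the start of study drug to Day 15. It sets no condition on the score before dosing, and requires neither worsening nor prior recovery. The same section defines organ failure-free days separately, as days on which the system scores 1 or less.

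Section 5.1 requires a failing organ at entry: "Patients must meet criteria for cardiovascular and/or respiratory dysfunction". In Table 2 the cardiovascular definition is low systolic pressure, or "mean arterial blood pressure ≤ 65 mmHg requiring vasopressors", despite fluids. For the lung, "Pulmonary dysfunction is defined as the patient requiring mechanical ventilation related to the septic process", together with a PaO2/FiO2 of 300 or less or an SpO2/FiO2 below 357. Stricter ratios apply when the lung is the primary site of infection. The first dose must be given within 24 hours of the qualifying failure.

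Table 1 schedules the modified SOFA score at screening, on Days 1 to 10 and at Day 15. Section 7.6.3 has the worst value of the day recorded. Section 12.2.7 uses the last assessment when none was collected.

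**The concern.** Sections 7.6.5 and 12.2.7 describe two different quantities. The first is new failure. The second is any failure seen after dosing, including failure that was there already. The entry criteria select patients whose cardiovascular or respiratory component is already at or above the recording threshold. For that system the rule mostly registers the reason for enrolment, which is unrelated to treatment.

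Because only the first occurrence is recorded, the entry failure also uses up the record. If the system recovers and then truly fails again, the second failure leaves no trace in this variable.

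At stake is a descriptive by-system account of organ failure arising on treatment. Organ function is part of secondary objective 3, and section 2.3 counts organ failure assessments among the important secondary endpoints. A reader who takes the summary at its section 7.6.5 description would read persisting failure as new failure.

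**Working it through.** **The plan's own figure.** The protocol gives no organ failure rates. Its only design figure is the power for ventilator-free days in section 13.4: 100 per group, difference 4.2, SD 11.380, one-sided 10%. Then 4.2 / (11.380 × √(2/100)) − 1.2816 = 2.610 − 1.282 = 1.328, which gives power of 90.8%; 97 per group would suffice for 90%. The stated 90% reproduces, and this point does not touch it.

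**Entry criteria set against the scoring table (Appendix G).**

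| Entry route (Table 2) | Modified SOFA component |
|---|---|
| Ventilated, PaO2/FiO2 ≤300 or SpO2/FiO2 <357 | Respiration 2 or more (same cut-offs) |
| Ventilated, lung the primary site, PaO2/FiO2 <200 or SpO2/FiO2 <214 | Respiration 3 or more |
| Hypotension requiring vasopressors | Cardiovascular 2 to 4 for every agent listed |

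The word *generally* is needed for the cardiovascular route. Appendix G counts adrenergic agents only when given for at least 1 hour, and low mean arterial pressure without a listed agent scores only 1.

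**From qualification to the first post-dose score.**
1. The first dose comes no later than 24 hours after the qualifying failure.
2. Day 1 runs from the first infusion to the end of that calendar day, and a score is scheduled on it.
3. The worst value of the day is used.
4. If no value is collected, the last one stands, so a pre-dose score can become a post-dose event without a new measurement. Section 13.3.5 also carries forward missing coagulation, liver and renal components.

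The qualifying system will therefore usually score above 1 at the first post-dose assessment. The same mechanism applies to any coagulation, liver or renal component already above 1 at screening. If the 14-day window is read as Days 2 to 15, by analogy with the 28-day period in section 12.2.6, the first counted day moves to Day 2 and the argument is unchanged.

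**Illustration for one system, on assumed rates.** Let b be the share of patients with the system above 1 at baseline and still above 1 at the first post-dose score. Let p be the risk of new failure in the rest. The recorded rate is b + (1 − b)p, so a true difference between arms shrinks by the factor (1 − b). Take p = 40% against 25%, a 15-point difference:

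| b | Recorded rates | Difference |
|---|---|---|
| 0.3 | 58.0% v 47.5% | 10.5 points |
| 0.8 | 88.0% v 85.0% | 3.0 points |
| 0.9 | 94.0% v 92.5% | 1.5 points |

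The fair comparator at b = 0.3 is the 70 patients per arm still at risk (100 × 0.7), not all 100. A hypothetical two-proportion test at one-sided 10% would have these powers:
- New failures only, 70 per arm, 40% v 25%: (0.150 − 1.2816 × 0.0792) / 0.0781 = 0.62, power about 73%.
- Rule as written, 100 per arm, 58.0% v 47.5%: (0.105 − 1.2816 × 0.0706) / 0.0702 = 0.21, power about 58%.

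The protocol plans no such test. The figures only show how persisting failure dilutes the record.

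**The case against.** The strongest reply is that nothing important depends on this record. The listed and formally analysed organ endpoint is organ failure-free days, which counts days and does not use a first event. Section 13.3.6 covers only the free-days variables, and section 13.3 specifies no incidence table for organ failure. This stands and keeps the point minor.

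It can also be said that at-risk rules for a descriptive variable belong in the statistical analysis plan. That would hold if the protocol were silent. Section 12.2.7 states a rule, and it does not match section 7.6.5.

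A reader might infer more than the documents support:
- *Nearly every patient would be an event on Day 1, so incidence would be close to 100% in each arm.* This needs an any-organ, patient-level composite that the protocol does not define; the rule works one system at a time. Entry does not put coagulation, liver or renal components above 1, nor both of the entry systems.
- *The screening score is collected but ignored.* Section 13.3.5 summarises change from baseline for each component and the total. Only the section 12.2.7 rule leaves it out.
- *The trial could not show new organ failure at all.* Treatment-emergent adverse events are defined against baseline and tabulated by arm, and laboratory shift tables are planned.
- *Occurrence of septic shock has the same fault.* Section 7.6.6 says only "Occurrence of septic shock will be collected as part of organ failure outcome data". It gives no derivation to fault, and the analysed variable is shock-free days.

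**Conclusion.** The contradiction between sections 7.6.5 and 12.2.7 holds, and the rule is wrong as written for its stated purpose. In every arm it will usually record the qualifying system, and any other system already above 1 at screening, as a post-entry failure at the first post-dose score. It also misses a later true recurrence in that system.

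Severity is minor. Systems scoring 1 or less at entry remain informative. Organ failure-free days, shock-free days, ventilator-free days and the sample size are unaffected, and the record is descriptive only.

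That entry failure meets the threshold follows from Table 2 and Appendix G, within the limits noted for the cardiovascular route. That it persists to the first post-dose score is an inference from the 24-hour window, worst-of-day scoring and carry-forward; the protocol gives no persistence rate. The numerical illustration rests wholly on assumed rates.

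**What to change.** In section 12.2.7, count post-entry failure of an organ system only when a post-dose component score is above 1 and either (a) the system scored 1 or less at baseline, or (b) it has had a recorded return to 1 or less since. Baseline can be the section 13.1 definition, the latest non-missing value before the first infusion. Leave the definition of organ failure-free days as it is.

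Summarise by system with the number at risk as denominator. It is cleaner to show (a) and (b) on separate lines. The first denominator is fixed before treatment. The second depends on recovery after randomisation and should be read with that in mind.

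The cost is a wording change and programming. Screening and daily scores are already scheduled in Table 1, so no new data are needed. The downside is smaller denominators, chiefly for the cardiovascular and respiratory systems.

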Optional blood sample for biomarker research	X ^j														
Optional blood sample for genetic research	X ^k														
24-hour volume status	X														
Physical examination; Lung auscultation, dermal examination	X ^l	(X) ^m	(X) ^m	(X) ^m	(X) ^m	(X) ^m	(X) ^m						X ⁿ		
Blood sample: clinical chemistry, haematology	X ^o	X ^p	X ^q	X ^p	X ^q	X ^p	X ^q	X ^p				X ^q		X	
Blood sample: coagulation parameters	X ^o	X ^p	X ^q	X ^p	X ^q	X ^p	X ^q	X ^p				X ^q		X	

Table 1 Study plan

Assessments	Screening	Treatment period ^b						Follow-up							
	Up to 0 h	D1 ^a	D2	D3	D4	D5	D6	D7	D8	D9	D10	D15±1 ^c	D29+2 ^c or WD	D29 ^c -6/+14	D90+14 ^d or WD
Urine sample: urinalysis	X ^o	X ^q		X ^q				X ^q				X ^q			
Protein C activity	X ^o														
Troponin I	X ^o		X ^q					X ^q							
HASA IgG and total HASA bridging assay	X ^o											X ^q	X ^q		
NAB assay	X ^o											X ^q	X ^q		
IgE	X ^o												(X ^{q,r})		
Procalcitonin	X ^{o,s}	X ^{q,s}	X ^q		X ^q			X ^q							
Lactate	X ^{o,s}	X ^s	X												
12-lead ECG		X ^t		X ^t		4-6 hours after last dose ^t					X		X ^t		
BP, PR, RR, temperature, blood O ₂ ^u	X	X	X	X	X	X	X	X	X	X	X	X			
PK ^v	X	X	X	X	X	12 hours after last dose					X				
Height	X														
Weight	X ^w						X ^w								
Modified SOFA Score ^x	X	X	X	X	X	X	X	X	X	X	X	X			
Glasgow Coma Score	X														
Pre-study and concomitant medication ^v	X	X	X	X	X	X	X	X	X	X	X	X			
Infection assessment	X ^z	X	X	X	X	X	X	X	X	X	X	X	X		

Table 1 Study plan

Assessments	Screening	Treatment period ^b						Follow-up								
	Up to 0 h	D1 ^a	D2	D3	D4	D5	D6	D7	D8	D9	D10	D15±1 ^c	D29+2 ^c or WD	D29 ^c -6/+14	D90+14 ^d or WD	
Randomisation	X															
Study drug administration ^a		X	X	X	X	X	X									
Pulmonary assessment	X	X	X	X	X	X	X	X								
Ventilator use	X	X	X	X	X	X	X	X	X	X	X	X	X			
Cytokines TNF α ^{aa}	X	X	X		X		X	X			X	X				
blood sample IL-6, IL-8 ^{ab}	X	X	X		X		X									
Multiplex assay ^{ac}	X	X	X		X		X	X			X	X				
Plasma renal panel ^{ac}	X	X	X		X		X	X			X	X				
7-day mortality, 28-day mortality ^{ad} , and mortality at Day 90									X				X ^{ad}			X
HRQoL ^{ac}													X ^{ac}			X ^{ac}

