7.6.3 Modified Sequential Organ Failure Assessment (SOFA) Scores

A modified SOFA score (ie, not including Glasgow Coma Score) will be calculated at each of the timepoints shown in [Table 1](#). For each of the following routine assessments, the worst value of the day will be recorded in the eCRF: $\text{PaO}_2/\text{FiO}_2$ (mmHg) or oxygen saturation by pulse oximetry ($\text{SpO}_2/\text{FiO}_2$) (mmHg), platelet count, bilirubin, vasopressor use ($\mu\text{g}/\text{kg}/\text{min}$, mmHg), and creatinine ([or urine output]). For laboratory values, use last available (if within 48 hours). On days when laboratory results are unavailable, values will be extrapolated from the previous available values. On days when laboratory results are unavailable, values will be extrapolated from the previous available values ([Section 13.3.5](#)).

The SOFA score for the cardiovascular component does not account for the use of phenylephrine or vasopressin as vasopressor medications. A cardiovascular component score of 3 will be assigned for phenylephrine doses of $\leq 300 \mu\text{g}/\text{kg}/\text{min}$ or vasopressin doses of

< 0.04 units/min. A cardiovascular component score of 4 will be assigned for phenylephrine doses of > 300 µg/kg/min or vasopressin doses of \geq 0.04 units/min.

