7.6.10 Shock-free days

The number of shock-free days will be recorded up to Day 15. Shock-free is defined as a score <2 taken from the cardiovascular component of the modified SOFA score (see Appendix G).

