12.2.8 Calculation and derivation of ICU-free days

The number of days alive and ICU-free up to and including Day 15 (over 14 days) will be derived from the assessment detailed in Section 7.6.9.

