12.2.9 Calculation and derivation of shock-free days

The number of shock-free days up to and including Day 15 (over 14 days) will be derived from the assessment detailed in Section 7.6.10.

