13.3.5 Modified Sequential Organ Failure Assessment (SOFA) Score

Summary statistics (mean, median, SD, minimum, and maximum) of the raw data and change from baseline to each scheduled study assessment for each component and the total modified SOFA Score will be presented by treatment group.

For missing coagulation, liver and renal of the total modified SOFA score, a LOCF approach will be used and the last assessment performed should be the value for that day. For cardiovascular and respiratory components, investigators will be encouraged to use other available data (on/off vasopressors, percentage oxygen saturation in order to complete the individual component score).

The worst BP and saturation values of the day should be used.

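### Organ failure-free and shock-free days have no rule for death and conflicting carry-forward limits, so on a literal reading patients who die can keep earning failure-free days

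*Protocol*

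**What the plan says.** Protocol 12.2.7 sets the organ failure rule: "Organ failure-free days will be designated for those days when the organ system modified SOFA score is" 1 or less. For gaps it says that "if a drug holiday or no value is collected, the last assessment performed should be the value for that day". Section 7.6.10 sets the shock rule: "Shock-free is defined as a score <2 taken from the cardiovascular component of the modified SOFA score". Section 12.2.9 adds only the window: "The number of shock-free days up to and including Day 15 (over 14 days) will be derived". None of these mentions death or survival.

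The neighbouring definitions do. Section 12.2.6 sets ventilator-free days (VFDs) to zero for a patient who dies before Day 29. Section 12.2.8 counts "The number of days alive and ICU-free up to and including Day 15".

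The limit on carrying values forward is stated in several ways:

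- Section 7.6.3: "For laboratory values, use last available (if within 48 hours". The next sentence extrapolates from earlier values with no limit.
- Appendix G, footnote a: the same 48-hour limit beside the same unlimited extrapolation.
- Section 12.2.7 and Table 1 footnote x: no limit.
- Section 13.3.5, for coagulation, liver and renal: "a LOCF approach will be used and the last assessment performed should be the value for that day", with no limit. For the cardiovascular and respiratory components it encourages investigators to complete the score from other data, such as whether the patient is on vasopressors.

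Section 13.1 lists both endpoints for formal analysis.

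**The concern.** When a patient has died, no value is collected. A programmer who follows 12.2.7 and 13.3.5 to the letter would fill the remaining days with the last score and count them as failure-free if that score was 1 or less. The arm with more early deaths would then collect more of this credit, so a survival benefit would count against the treatment on these endpoints.

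The conflicting limits add to this. The days with no scheduled data lie mostly in the second week, and the choice between 48 hours and no limit decides whether the laboratory-based organs have any value on most of those days. Section 2.3 counts shock-free days and organ failure assessments among the important secondary endpoints, and 2.2 puts organ dysfunction in the research hypothesis.

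**Working it through.** **1. Reading the laboratory schedule.** Table 1 marks clinical chemistry and haematology at screening, Days 2, 4, 6 and 15, and Day 29. Days 1, 3, 5 and 7 carry footnote p, which allows recording only if a result exists anyway. Study-drawn samples: 1 (screening) + 4 (Days 2, 4, 6, 15) + 1 (Day 29) = 6. Table 6 also gives 6 samples for each, so the reading is confirmed.

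**2. Unscheduled days.** The window is taken as Days 2-15, which is 14 days. Taking Days 1-14 leaves the two counts below unchanged.

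- SOFA is marked on Days 1-10 and 15, so Days 11-14 are missing: 4/14 = 29%.
- Laboratory tests have no mark on Days 8-14: 7/14 = 50%. This concerns coagulation, liver and renal only, because the shock-free rule uses no laboratory value.

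**3. What the conflicting limit does.** With no limit, laboratory scores on Days 8-14 rest on the Day 6 value, or Day 7 if one exists. With a 48-hour limit they stop at Day 8 or Day 9. That leaves Days 9-14 (6 of 14) or Days 10-14 (5 of 14) with no value, and the protocol does not say how such a day counts.

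**4. Where the death rule sits.** Section 13.3.6 says these endpoints are handled as VFDs are, and points to 13.3.4. That section contains last-observation-carried-forward for missing data. The zero-for-death rule is in 12.2.6, which is not cited. So the cross-reference brings in carry-forward but not clearly the death rule.

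**5. Credit per death.** For a death on Day t with a last component score of 1 or less, up to 15 - t further days are credited: 12 for Day 3, 10 for Day 5, 8 for Day 7, 5 for Day 10.

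**6. Effect on an arm mean, per component.** The protocol gives neither mortality by Day 14 nor component scores before death, so all inputs here are assumed. Inflation = (fraction dead by Day 14) x (fraction of those with last score of 1 or less) x (days credited).

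- Low: 0.10 x 0.25 x 5 = 0.125, about 0.1 days.
- Middle: 0.20 x 0.50 x 8 = 0.8 days.
- High: 0.30 x 0.75 x 10 = 2.25, about 2.3 days.

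**7. Effect on the between-arm difference.** Section 2.4 cites 28-day mortality of 37% and 26% from the earlier Phase IIb study, a gap of 11 points, taken here as an upper bound for the gap by Day 14.

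- Low: 0.11 x 0.25 x 5 = 0.14, about 0.1 days.
- High: 0.11 x 0.75 x 10 = 0.83, about 0.8 days.

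**8. If the 48-hour limit governed.** At most 2 days could be credited after death for a laboratory component. The arm-mean inflation would be at most 0.30 x 0.75 x 2 = 0.45 days, and the shift in the difference at most 0.11 x 0.75 x 2 = 0.17 days.

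**The case against.** The strongest reply is that no sentence carries a score past death. The sentence in 12.2.7 opens with blood pressure and saturation and reads naturally as a rule for missed assessments in patients under observation. Scoring of death in a derived secondary endpoint is often settled in the statistical analysis plan, which is not shown. It stands that the protocol does not state carry-forward past death. That is an inference from a literal rule and silence, and a reader should not report it as the sponsor's declared intention. But the protocol does fix a derivation here, 13.3.5 gives the laboratory components the same unlimited rule, and the two adjacent endpoints do address death.

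The shock-free part is also weaker than it looks. Every listed vasopressor or inotrope scores at least 2 in Appendix G, so a patient who dies on one carries a failing score and earns nothing. Section 6.5.2 records medication start and stop dates to Day 29, and 13.3.5 allows vasopressor status to complete the score, so shock on Days 11-14 can largely be derived. This stands, although the shock-free definition does not refer to those records. A patient who dies off these drugs scores at most 1 even if hypotensive, so the gap is not fully closed.

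A reader might infer that half the window is unmeasured for both endpoints. The documents do not support that. The 7/14 applies to the three laboratory-based organs; for shock-free days and the respiratory component it is 4/14. In addition, unscheduled does not mean unmeasured, because routine-care results may exist.

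A reader might also credit every early death with failure-free days. That would require every patient who dies to have a last component score of 1 or less, which nothing in the protocol supports.

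**Conclusion.** The point holds as a defect in definition. Two formally analysed secondary endpoints lack the alive condition that their neighbours have, and the stated gap rule, followed literally, credits days after death. The effect is likeliest for coagulation, liver and renal. The carry-forward limit contradicts itself within 7.6.3 and Appendix G, and both conflict with 12.2.7 and 13.3.5.

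On the assumed inputs, with no time limit and counting each organ separately, an arm mean rises by about 0.1-2.3 days per component. The between-arm difference moves by about 0.1-0.8 days against the arm with better survival. The 48-hour reading would make both much smaller for the laboratory components.

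It does not follow that the trial's main conclusion is at risk. VFDs score death as zero, ICU-free days require survival, mortality is analysed separately, and the sample size rests on VFDs alone (13.4). For secondary endpoints in an exploratory Phase IIb study, this should be fixed but is not critical.

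**What to change.** - In 7.6.10, 12.2.7 and 12.2.9, define both endpoints as days alive and free of organ failure or shock, with every day from death onward counted as not free.
- State one carry-forward limit, in the same words, in 7.6.3, 12.2.7, 13.3.5, Appendix G and Table 1 footnote x. Say that nothing is carried past death and how a day beyond the limit is counted.
- For shock-free days, derive vasopressor status on Days 11-14 from the medication start and stop dates already recorded to Day 29.
- For coagulation, liver and renal, use routine-care laboratory results where they exist on Days 8-14.

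The cost is protocol wording and a little more data abstraction, with no added procedures. Reported failure-free days will be somewhat lower, because days after death no longer count.
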